8.4.7. Rescue Medication Usage

Use of rescue medication is recorded on the daily diary. In the event of prolonged seizures or status epilepticus, rescue medication is administered according to each subject's personalized regimen consisting of one or more medications. If the first rescue administration does not control the seizures, a second or even third round might be administered. They second and third round might use different medications or different doses than the first round of rescue meds.

Rescue medication will be summarized by treatment group and comparisons of active treatment vs. Placebo for the following:

• The number of days rescue medication was taken (normalized to 28 days) will be summarized separately for the Baseline and T+M periods by the mean (SD) as well as the median, minimum and maximum values. Multiple medications taken on the same day will be counted once for that day. The ZX008 group will be compared to the placebo group using a non-parametric ANCOVA analogous to that described in the primary efficacy endpoint section. Specifically, the rank ANCOVA will use the ranks of rescue medication frequency during T+M or M period as the response, and will incorporate treatment group as a factor and the ranks of rescue medication frequency during Baseline as a covariate.

The number of medications used per episode will be summarized using similar descriptive statistics as above. Rescue medications related to an episode of SE are considered to be all rescue administered on the day of the SE (or seizure lasting >10 min). If more than one episode of SE or a seizure lasting >10 min occurred in a single day, the rescue medication for that episode is all rescue administered after the seizure until the start time of the next prolonged seizure.

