4.3. TREATMENT ASSIGNMENT & BLINDING

Upon completion of the Baseline Period in Part 1, subjects who qualified for the study were randomized (1:1:1) in a double-blind manner to receive 1 of 2 doses of ZX008 (0.2 mg/kg/day, 0.8 mg/kg/day; 30mg/day maximum [0.2 mg/kg/day or 0.5 mg/kg/day; 20 mg/day maximum for subjects taking concomitant STP]) or placebo. The randomization was stratified by weight (<37.5 kg, $\ge37.5 \text{ kg}$) to ensure balance across treatment arms, with a target of at least 25% in each weight group. Subjects were assigned a randomization number by the IWR system upon confirmation that the subject qualified for enrollment in the Titration Period.

The primary biostatistical team, data management team, and clinical team will remain blinded to subject treatment assignments until approval is given for the unblinding of the Part 1, Cohort A database and finalization of inclusion in the study populations is made.

The release of unblinded pharmacokinetic concentration data, ECG and ECHO data to facilitate external analyses will be completed only after the approval for unblinding of the Part 1 database by Zogenix.

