8.2.2. Part 1 Primary Efficacy Endpoint Analyses

T+M Period:

The primary analysis will compare the ZX008 0.8 mg/kg/day group to the placebo group for Cohort A using a two-sided test at the α =0.05 level of significance.

The primary endpoint will be analyzed using a non-parametric analysis of covariance (ANCOVA) model with treatment group (three levels; Placebo, 0.2 mg/kg/day, 0.8 mg/kg/day) and weight strata group (< 37.5 kg, \geq 37.5 kg) as factors, rank of baseline DSF_B as a covariate and rank of percent CDSF_{T+M} as response. Treatment group mean differences from placebo will be estimated via least squares means from the analysis model along with 95% confidence intervals.

The null hypothesis

$$H_0$$
: $\mu_{Z0.8} - \mu_P = 0$,

will be tested against the alternative

$$H_A$$
: $\mu_{Z0.8} - \mu_P \neq 0$,

where $\mu_{Z0.8}$ and μ_P represent the ZX008 0.8 mg/kg and Placebo group location parameter, respectively.

Rejection of the null hypothesis in favor of the alternative, in the presence of a statistically significantly smaller seizure frequency for the treatment group compared to the placebo group, (two-sided p-value <.05) will be regarded as evidence of a treatment benefit in favor of the 0.8 mg/kg group. A similar comparison of the location parameter for Z008 0.2 mg/kg/day vs. placebo will be regarded as evidence of a treatment benefit of the 0.2 mg/kg group. This is the 3rd key secondary endpoint.

Sample SAS code for the non-parametric ANCOVA described above is as follows:

```
Proc rank data=temp ties=mean out=ranktemp;
Var bsrd csrd;
Rank r_bsrd r_csrd;
Run;
proc glm data=ranktemp;
    class wtgrp trtp;
    model r_csrd = r_bsrd wtgrp trtp / SS3;
    lsmeans trtp / pdiff stderr;
```

where trtp = randomized treatment group (with codes 1, 2, 3 indicating placebo, 0.2 mg/kg, and 0.8 mg/kg groups).

```
r_bsrd = rank of baseline DSF_B,
r_csrd = rank of percent CDSF_{T+M}
wtgrp = weight group.
```

Additional statements may be used to obtain estimates and associated 95% confidence intervals.

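### The terms listed for the rescue-medication rank ANCOVA (8.4.7) omit the weight stratum used in the randomisation and the primary model; if weight predicts rescue use, the test loses some power

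*SAP*

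**What the plan says.** Section 8.4.7 compares days with rescue medication, normalised to 28 days, between ZX008 and placebo "using a non-parametric ANCOVA analogous to that described in the primary efficacy endpoint section". It then says specifically what that means. The response is the rank of rescue frequency in T+M or M, and the model "will incorporate treatment group as a factor and the ranks of rescue medication frequency during Baseline as a covariate". Weight does not appear.

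The primary model in section 8.2.2 has treatment and weight stratum as factors and the rank of baseline seizure frequency as covariate. The sample SAS code agrees: "model r_csrd = r_bsrd wtgrp trtp / SS3", where wtgrp is the weight group.

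Section 4.3 gives the design: subjects "were randomized (1:1:1) in a double-blind manner". "The randomization was stratified by weight", with the cut at 37.5 kg and "with a target of at least 25% in each weight group".

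The stratum is also used in the responder logistic regression (8.2.4) and in the Cochran-Mantel-Haenszel test of CGI-I (8.3.1). Section 11, on changes from planned analyses, does not mention leaving it out for rescue medication.

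**The concern.** There are two issues. The first is wording. The reference to the primary model points to an analysis with the stratum, while the list of terms points to one without it. Two programmers could each follow section 8.4.7 and report different p-values.

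The second is statistical. Stratified allocation balances the arms on weight by design. If weight also predicts the outcome, a model without it leaves the between-stratum variation in the error term, although that variation no longer contributes to the treatment difference. The reported standard error is then too large, so the actual type I error falls below the nominal level and power is lost. What is at stake is the calibration and sensitivity of an exploratory p-value.

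**Working it through.** **The plan's own figures.** The SAP states no power or type I error for the rescue-medication test. Its sample size concerns the primary endpoint (section 4.2: difference 30, SD 50, two-sided 0.05, 90% power). It reproduces:

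- Normal approximation: 2 × (1.96 + 1.2816)² × 50² / 30² = 58.4, so 59 per group; the t-test version gives 59.35.
- Nonparametric: 59.35 / (3/π) = 62.2, so 63.
- 20% dropout: 63 / 0.8 = 78.75, so 79 per group, and 3 × 79 = 237.

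These figures do not depend on the present point. They supply a realistic trial size.

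**Analytic check.** Let r² be the share of response variance, after baseline adjustment, that is due to the weight stratum. The SAP gives no value, so 0 to 0.20 is an assumed range. Without the stratum the standard error is overstated by 1/√(1 − r²), which gives:

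- type I error = 2 × (1 − Φ(1.96 / √(1 − r²)))
- power = Φ(3.2415 − 1.96 / √(1 − r²)), anchored at 90% with the stratum in the model (1.96 + 1.2816 ≈ 3.2415)

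For example, at r² = 0.10, 1.96 / √0.90 = 2.066. Type I error is 0.039 and power is Φ(1.1755) = 88.0%.

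**First simulation.** 237 subjects, 1:1:1 in permuted blocks within stratum, near-continuous responses, rank ANCOVA with and without the stratum, and 50% or 25% of subjects in one stratum. There were 6,000 runs for type I error and 4,000 for power. Power with the stratum was about 76 to 77%.

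| r² (assumed) | Analytic type I error, no stratum | Analytic power, no stratum (90% with) | Simulated type I error, no stratum (50% / 25% share) | Simulated power loss, points |
|---|---|---|---|---|
| 0 | 0.050 | 90.0% | 0.047 / 0.051 | 0 |
| 0.01 | 0.049 | 89.8% | 0.048 / 0.048 | 0.3 |
| 0.05 | 0.044 | 89.1% | 0.047 / 0.044 | 1.6 to 1.8 |
| 0.10 | 0.039 | 88.0% | 0.043 / 0.040 | 3.3 to 3.6 |
| 0.20 | 0.028 | 85.3% | 0.029 / 0.032 | about 7 |

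With the stratum in the model, simulated type I error was 0.047 to 0.053 at every r². The simulated losses exceed the analytic ones because power starts lower (76 to 77% rather than 90%).

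**Second simulation.** Over-dispersed counts, three arms of 83, stratified allocation, 4,000 runs per setting. Rescue use was assumed to differ between strata as shown.

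| Fold difference by stratum, baseline / T+M | Type I error, no stratum | Power without | Power with | Loss, points |
|---|---|---|---|---|
| none | not tabulated | 67.1% | 67.2% | 0.1 |
| 1.35 / 1.5 | 4.9% | 68.7% | 69.5% | 0.8 |
| 1.8 / 2.2 | 4.4% | 69.8% | 71.6% | 1.8 |
| 2.7 / 3.7 | 3.9% | 68.0% | 73.5% | 5.5 |

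The Monte Carlo standard error of a 5% rate over 4,000 runs is √(0.05 × 0.95 / 4,000) = 0.34 points. So 4.9% and 4.4% are each within two standard errors of 5%, and 3.9% is not.

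The calculations agree in pattern: no loss without a stratum effect, and a loss that grows with the effect. A large share of tied zeros, which rescue-day data may contain, was not examined separately.

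**The case against.** The strongest reply is that section 8.4.7 is shorthand. It names what is specific to rescue medication and leaves the rest to the primary model. The SAP does this elsewhere: section 8.2.1 describes the primary analysis as adjusted for baseline frequency without mentioning weight, and 8.2.2 then includes it. Section 8.4.3 is equally brief about seizure-free days. That reading is possible. But 8.4.7 goes further than those sections by setting out response, factor and covariate after saying it is being specific, so the literal model is the one without weight. At the least, the text has two readings.

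A reader might infer that the test is certainly conservative and underpowered. The documents do not support that. Both effects require weight to predict rescue use after baseline adjustment, and the SAP gives no figure for this. The 37.5 kg cut equals 30 mg/day ÷ 0.8 mg/kg/day, so the stratum may reflect the dose cap rather than prognosis. The largest simulated losses come from the strongest assumptions.

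A reader might also infer that 8.4.7 promises an exact copy of the primary model. It says only that the two are analogous, and the responses already differ: rank of on-treatment frequency here, rank of percent change in 8.2.2.

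Finally, other tests in the SAP ignore weight, such as the Wilcoxon tests (8.2.3, 8.4.4) and the Fisher tests (8.4.6, 8.4.8). That is true, but those methods have no covariate terms. Here a model with a place for the stratum is already being fitted.

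**Conclusion.** The point holds as a free improvement of low impact. As listed, the model in 8.4.7 leaves out the stratum that the trial randomised by and that the model it refers to contains, without a stated reason.

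The size is conditional. Under assumed stratum effects, the power lost is about 0 to 2 points for weak effects (r² up to 0.05, or up to a 2.2-fold difference in T+M) and about 3 to 7 points for stronger ones. Type I error falls below 5% and never rises above it because of the omission. If weight is not prognostic, the two models perform alike.

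It would be wrong to read this as a threat to the trial's conclusions. Days with rescue medication is an exploratory endpoint (section 5.5) and is not among the six ordered tests in section 8.1. The 0.05 level in section 6.6.1 is set for primary and secondary endpoints, and no power is claimed for this one. Only a nominal exploratory p-value is affected.

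**What to change.** In section 8.4.7, list weight stratum (<37.5 kg, ≥37.5 kg) as a factor beside treatment and the rank of baseline rescue frequency, for both the T+M and the M analyses, as in section 8.2.2. This takes a few words in the SAP and one term in the model. With no stratum effect, simulated power was 67.1% without the term and 67.2% with it, so including it costs nothing measurable. It also removes the double reading. If the stratum is left out on purpose, the section should say why.

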8.4.8. Incidence of Medical Services to Treat Seizures

Data on hospitalization and healthcare resource use to treat seizures will be captured in the CRF and will be used to calculate incidence.

Details of the hospitalizations, including reasons for hospitalization and use of resources will be summarized. The number and percentage of subjects who utilized medical center care to treat a seizure will be presented by treatment group for the T+M period. The mean, median, min and max describe the number of events or procedures per subject for those subjects who had at least one event or procedure.

Statistical comparisons of the incidence of use of medical services between active and placebo groups will be provided using Fisher's exact test.

8.4.9. Vineland Adaptive Behavior Scale (VABS)

The VABS is a parent/caregiver completed assessment that looks at the personal and social skills of individuals from birth through adulthood (Sparrow, S. S. & Cicchetti, D. V. (1989)). Because adaptive behavior refers to an individual's typical performance of the day-to-day activities required for personal and social sufficiency, these scales assess what a person actually does, rather than what he or she is able to do. The VABS assesses adaptive behavior in 4 domains:

- Communication
- Daily living skills
- Socialization
- Motor skills

In Part 1, the VABS is collected at Visit 3 (Randomization), Visit 8 (Day 43), and Visit 12 (End of Study/Early Termination).

At each assessment, the standardized domain scores will be determined.

For each domain, the change from baseline for each subject will be calculated by subtracting the domain score measured at Baseline from the analogous score measured at Visit 8 (Day 43) and Visit 12 (End of Study /Early Termination). Observed values and change from baseline will be summarized by descriptive statistics. The difference between treatment groups will be assessed using pairwise Wilcoxon rank-sum tests on the change from baseline.

The individual item outcomes and standardized domain scores will be presented in the subject data listing.

8.4.10. Quality of Life in Childhood Epilepsy (QOLCE) Scale

The parent/caregiver will complete the QOLCE. This assessment looks at how epilepsy affects day-to-day functioning of their child in various life areas, including physical activities, well-being, cognition, social activities, behavior and general health (Sabaz et al., 2000; Talarska 2007). There is also one question on overall quality of life, administered as part of the QOLCE.

The QOLCE is collected at Visit 3 (Randomization) and at Visit 12 (End of Study/Early Termination).

The QOLCE scores items with a possible 5-point response. To calculate subscale scores, the 5-point item scores will first be reverse coded as necessary so that scores of 5 represent the best possible response and 1 represents the worst possible response. [Details of the reverse coding are provided in the shells for the TLFs]. Item scores will then be transformed to a 0-100 scale as follows: 1 -> 0, 2 -> 25, 3 -> 50, 4 -> 75, 5 -> 100. After transformation, a score for each subject for each subscale is calculated by averaging that subject's responses to each item in the subscale. A value of 0 represents the lowest or poorest score and 100 reflects the highest level of functioning. The 16 subscale scores per subject are then averaged to obtain an overall quality of life score for each subject.

Summary descriptive statistics including the n, mean, standard deviation, median, minimum, and maximum will be generated for the index score at each scheduled collection time point.

A higher subscale and overall quality of life score, indicates a better response.

Table 6: Subscale of QOLCE:

Domain	Subscale	Item
Section 3: Physical	Physical Restrictions	3.1 a-j
Section 3: Physical	Energy/Fatigue	3.2 a,b
Section 4: Well-being	Depression	4.1 a,d,e,l
Section 4: Well-being	Anxiety	4.1 b,g,j,n,o,p
Section 4: Well-being	Control/helplessness	4.1 c,f,h,i
Section 4: Well-being	Self-esteem	4.1 k,m,q,r,s
Section 5: Cognition	Attention/Concentration	5.1 a,d,e,f,g
Section 5: Cognition	Memory	5.1 j,k,l,m,n,o
Section 5: Cognition	Language	5.1 p,q,r,s,t,u,v,w
Section 5: Cognition	Other Cognitive	5.1 b,c,h
Section 6: Social Activities	Social Interactions	6.1 c,f,h
Section 6: Social Activities	Social Activities	6.1 a, e, 6.2
Section 6: Social Activities	Stigma Item	6.1 i
Section 7: Behavior	Behavior	7.1 a,
		c,f,g,h,i,j,k,l,m,o,q,r,s,t
Section 8: General Health	General Health	8.1

Version 2.0

Syneos Health #1009529A

Section 2 (USA Version) or	Quality of Life Item	2.1 or 9.1
Section 9 (Australia Version):		
Quality of Life		
Overall Quality of Life *		Average of 16 subscale scores*

^{*}An Overall Quality of Life Score will be computed by adding each subscale score for each individual and then dividing by 16.

[figure not shown]
For each treatment group and at each schedule visit, the descriptive statistics will be presented for each QOLCE subscale and for the overall quality of life score.

[figure not shown]
In addition, the change from baseline in the overall QOLCE will be calculated for each subject by subtracting the Part 1 baseline score from the score measured at each scheduled post-baseline visit. The change from baseline for each treatment group will be summarized by summary statistics. Treatment groups will be compared using pairwise Wilcoxon Rank-sum tests.

Individual subject data for the domains will be listed.

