The exploratory endpoints for Part 1 of the study are:

- The change from baseline in behavior using the Vineland Adaptive Behavior Scale (VABS)
- The change from baseline in quality of life (QoL) using the Quality of Life in Childhood Epilepsy (QOLCE)
- The change from baseline in caregiver burden using the Zarit Caregiver Burden Inventory
- The change from baseline in affective symptoms of parent/caregiver using the HADS scale
- Incidence of status epilepticus in the M and T+M period.
- Incidence of rescue medication usage in the T+M and M periods
- Number of days rescue medication used in the T+M and M periods
- Incidence in use of medical services to treat seizures in the M and T+M periods

ANALYSIS SETS

Separate analysis data sets will be produced for Cohort A and Cohort B. Cohort A will include subjects from North America, Europe, and Australia; Cohort B will include subjects from Japan.

Syneos Health #1009529A

6.1. **ENROLLED POPULATION**

The enrolled population is defined as all subjects who signed the informed consent form. This population will be used for listings.

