8.4.3. Seizure-Free Days

Seizure free days will be taken from the parent/caregiver diary data.

A seizure free day with no seizures leading to drops will be defined as a day for which diary data are available and with no ESC-defined drop seizures. A day without countable motor seizures will be defined as a day for which diary data are available and with no countable motor seizures. The total number of countable seizure-free days and drop seizure-free days will be summed for the entire T+M period and similarly for the baseline period.

Seizure-free days per 28 days at baseline = (number of seizure free days during baseline)*28/ (number of days during baseline with non-missing diary data)

Seizure-free days per 28 days during T+M Period = (number of seizure free days during T+M Period)*28/ (number of days during T+M Period with non-missing diary data)

Statistical comparison of treatment groups and placebo on the number of seizure free days per 28 days and drop seizure-free days per 28 days during T+M using the baseline as covariate will be done with a similar non-parametric ANCOVA model as described for the primary analysis.

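### Change in the overall QOLCE score is tested without the baseline score or weight stratum, a valid but less precise choice than the rank ANCOVA the plan uses elsewhere

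*SAP*

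**What the plan says.** Section 8.4.10 sets the timing: "The QOLCE is collected at Visit 3 (Randomization) and at Visit 12 (End of Study/Early Termination"). There is thus one baseline and one post-baseline score. The change in the overall score is formed by "subtracting the Part 1 baseline score from the score measured at each scheduled post-baseline visit", and then "Treatment groups will be compared using pairwise Wilcoxon Rank-sum tests". No covariate or stratum is named and no reason is given.

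Other sections treat baseline differently:

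- Section 8.2.2 (primary endpoint): non-parametric ANCOVA with treatment and weight stratum as factors and "rank of baseline DSF_B as a covariate".
- Section 8.4.3 (seizure-free days): the comparison "using the baseline as covariate will be done with a similar non-parametric ANCOVA model as described for the primary analysis".
- Section 8.4.7 (days with rescue medication): rank ANCOVA with treatment as a factor and "the ranks of rescue medication frequency during Baseline as a covariate".

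Section 4.3 says that randomisation was stratified by weight. QOLCE and rescue medication are both listed as exploratory endpoints in section 5.5. Neither is in the six-step hierarchy of section 8.1.

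**The concern.** A change score fixes the baseline coefficient at 1. When baseline and follow-up correlate imperfectly, the best coefficient is smaller, so differencing over-corrects: subjects with low baselines tend to rise and those with high baselines to fall. That adds noise to the comparison. It also lets a chance difference in baseline means carry through, with opposite sign, into the observed difference in change.

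What is at stake is the precision of the plan's subject quality-of-life comparison. An imprecise null result could be misread as absence of effect. The covariate is already collected and the model is already written for other endpoints, so the precision is given up without a stated reason. Exploratory status does not explain it, since rescue medication has the same status and gets the adjusted model.

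**Working it through.** **The plan's own figures.** The SAP has no sample size, effect, SD, correlation or power for QOLCE. Its only power statement (section 4.2) concerns drop seizures: difference 30, SD 50, two-sided 5%, 90% power. The normal formula gives 2 × (50 × (1.960 + 1.282) / 30)² ≈ 58.4. The t-based figure is 59.35, and dividing it by the Wilcoxon efficiency 3/π gives 62.2, rounded up to 63 as stated. Then 63 / 0.8 = 78.75, rounded up to 79, and 3 × 79 = 237. These reproduce but say nothing about QOLCE.

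**Relative precision.** Let rho be the correlation between the Visit 3 and Visit 12 scores, and assume equal variances, scaled to 1.

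- Variance of the change score: 2(1 − rho).
- Variance after regression on baseline: 1 − rho².
- Ratio, adjusted to change: (1 − rho²) / [2(1 − rho)] = (1 + rho)/2, which is below 1 whenever rho < 1.

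**Effect of a chance imbalance.** Given the baseline, the expected change has slope rho − 1. A baseline difference of δ between arms shifts the unadjusted difference in change by (rho − 1)δ: half of δ at rho 0.5 and a fifth at rho 0.8, in the opposite direction.

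**Power.** If the unadjusted test has power P0, adjusted power is Φ[(1.960 + z(P0)) / √((1 + rho)/2) − 1.960]. With P0 = 80%, z = 0.842. At rho 0.5 this is Φ(2.802 / 0.866 − 1.960) = Φ(1.275) = 89.9%.

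Gain in percentage points, with rho and P0 both assumed:

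| rho | Variance ratio | P0 = 50% | P0 = 80% | P0 = 90% |
|---|---|---|---|---|
| 0.3 | 0.65 | 18.1 | 13.5 | 8.0 |
| 0.5 | 0.75 | 11.9 | 9.9 | 6.3 |
| 0.7 | 0.85 | 6.6 | 6.0 | 4.0 |
| 0.8 | 0.90 | 4.2 | 4.0 | 2.7 |
| 0.9 | 0.95 | 2.0 | 2.0 | 1.4 |

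**Check with the rank methods themselves.** This was a simulation with 79 per arm, bivariate normal scores and 1,500 replicates, with the effect set so that the Wilcoxon test had about 80% power. It compared the Wilcoxon test on change with rank ANCOVA of change on ranked baseline:

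- rho 0.3: 78.6% against 93.5%
- rho 0.5: 78.7% against 88.1%
- rho 0.7: 78.5% against 84.8%
- rho 0.8: 80.3% against 84.2%
- rho 0.9: 80.7% against 81.4%

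The gains of 14.9, 9.4, 6.3, 3.9 and 0.7 points follow the formula within simulation error. Base power was an input, so the simulation confirms the relation between the two tests, not the actual power for QOLCE. It also ignores the 0–100 bounds of the score and uses the per-arm number before dropout.

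**The case against.** The strongest reply is that nothing here is invalid. A pre-specified rank-sum test on change is a proper randomised comparison, QOLCE is exploratory, and the SAP claims no power for it. That stands, and it limits the point to a minor one.

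A second reply is that the plan has a pattern: rank ANCOVA for diary counts and Wilcoxon for scales, as with the Vineland scale (VABS) in section 8.4.9. This stands in part. QOLCE is not the only exception, and the analysis text for the Zarit and HADS scales is not visible in the copy at hand, so QOLCE cannot be called an outlier among the questionnaires. But the pattern gives no reason to leave out an available baseline. The addendum also reports that the planned VABS analyses were not completed. The longest drop-free interval (section 8.4.4) uses Wilcoxon too, but it is defined over titration plus maintenance only and has no baseline to adjust for.

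A reader might infer more than the SAP supports:

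- **A fixed loss of about 10 points of power.** This needs a correlation near 0.5 and base power near 80%, and the SAP gives neither. The overall score averages 16 subscales, so a higher correlation, and hence a smaller gain, is at least as plausible; that too is an assumption.
- **A biased comparison.** Over randomisation it is unbiased and its type I error is unaffected. Imbalance matters only conditionally on the realised baselines.
- **Baseline imbalance left uncorrected.** Baseline is subtracted. What is missing is the regression adjustment.

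**Conclusion.** The point holds as a minor matter of efficiency. Section 8.4.10 uses a valid test that is less precise than the adjusted model specified for the primary endpoint, seizure-free days and rescue-medication days. If unadjusted power is 80%, adjustment gains about 2 points (rho 0.9) to 14 points (rho 0.3). Letting base power vary from 50% to 90% as well, the range is about 1 to 18 points. These figures rest on assumed correlations, assumed base power, equal variances and approximate normality. The weight stratum contributes nothing to them; including it simply matches the randomisation. No confirmatory conclusion is affected.

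**What to change.** In section 8.4.10, specify the section 8.2.2 non-parametric ANCOVA for the overall QOLCE score: rank of change as response, rank of baseline QOLCE as covariate, treatment and weight stratum as factors. Keep the pairwise Wilcoxon tests as supportive. Where Cohort A is already unblinded (the addendum describes post-hoc analyses after its database lock), leave the planned Wilcoxon result in place and report the adjusted analysis as a labelled supportive one. The cost is one sentence of SAP or addendum text and reuse of existing code. No new data are needed and the testing hierarchy does not change.
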